8.2.4 Lead measurements (pacing thresh., sensing ampl., shock imp., lead imp.)

CIP chapter 8.1.4.15 Lead measurements with Renamic programmer at implantation and each follow-up

The system performance, i.e. appropriate sensing and pacing is evaluated at the end of the implantation procedure and at the end of each follow-up by either manually or automatically triggered lead measurements ...

The following "lead measurements" analyses have to be performed for implantation, Pre-Hospital Discharge, 3m follow-up, 6m follow-up, and 12m follow-up, whereby the variables labels have to be indicated, respectively.

Data file, identifier PRVISIT & patient_display_id_full	Notes	Variable name	Variable label	Variable level	Nominal values
lead_measurement	No report	PRVISIT	Visit	nominal	
  Implantation  Pre-Hospital Discharge  3m Follow-up  6m Follow-up  12m Follow-up

Lead measurements /Right Atrium (RA)

Data file PRVISIT & patient_display_id_full	Notes	Variable name	Variable label	Variable level	Nominal values
lead_measurement	descr.	DURAMNA	No RA lead measurements available	nominal	
  RA lead measurements not done  RA lead not implanted/not active
	descr.	DURAMRH	RA rhythm during sensing measurements	nominal	
  Sinus rhythm  Atrial fibrillation  Atrial flutter/other SVT  Atrial paced rhythm  Other  Unknown
	descr.	DURASA	RA sensing amplitude [mV], mean value	scale	n.a.
	descr.	DURAPT	RA pacing threshold [V]	scale	n.a.
	descr.	DURAPTPW	Pulse width for RA pacing threshold measurements [ms]	scale	n.a.
	descr.	DURAPI	RA pacing impedance [Ω]	scale	n.a.

Lead measurements / Right Ventricle (RV)

Data file PRVISIT & patient_display_id_full	Notes	Variable name	Variable label	Variable level	Nominal values
lead_measurement	descr.	DURVMNA	No RV lead measurements available	nominal	
  RV lead measurements not done  RV lead not implanted/not active
	descr.	DURVMRH	RA rhythm during sensing measurements	nominal	
  Intrinsic – atrial conducted  Ventricular paced rhythm  Other atrial conducted  Ventricular paced rhythm  Other
	descr.	DURVSA	NEW: RV sensing amplitude [mV], mean value	scale	n.a.
	descr.	DURVPT	RV pacing threshold [V]	scale	n.a.
	descr.	DURVPTPW	Pulse width for RV pacing threshold measurement [ms]	scale	n.a.
	descr.	DURVPI	RV pacing impedance [Ω]	scale	n.a.
	descr.	DURVSI	Painless shock impedance [Ω]	scale	n.a.

Lead Measurements / Left Ventricle (LV)

Data file PRVISIT & patient_ display_id_full	Notes	Variable name	Variable label	Variable level	Nominal values
lead_ measurement	descr.	DULVMNA	No LV lead measurements available	nominal	
 ◦ LV lead measurements not done ◦ LV lead not implanted/not active
	descr.	DULVTYP	type of LV lead	nominal	
 ◦ Bipolar ◦ Quadripolar
		DULVSV	Permanently (first) programmed LV sensing vector	nominal	
 ◦ LV1 tip to LV2 ring (bipolar) ◦ LV1 tip to Can (unipolar) ◦ LV2 ring to LV3 ring ◦ LV2 ring to Can ◦ LV3 ring to LV4 ring ◦ LV3 ring to Can ◦ LV4 ring to Can
	descr.	DULPV01	Permanently programmed (first) LV pacing vector	scale	
 ◦ LV1 tip to LV2 ring ◦ LV1 tip to LV3 ring ◦ LV1 tip to LV4 ring ◦ LV1 tip to RV coil/ring ◦ LV1 tip to Can ◦ LV2 ring to LV1 tip ◦ LV2 ring to LV3 ring ◦ LV2 ring to LV4 ring ◦ LV2 ring to RV coil/ring ◦ LV2 ring to Can ◦ LV3 ring to LV1 tip ◦ LV3 ring to LV2 ring ◦ LV3 ring to LV4 ring ◦ LV3 ring to RV coil/ring ◦ LV3 ring to Can ◦ LV4 ring to LV1 tip ◦ LV4 ring to LV2 ring ◦ LV4 ring to LV3 ring ◦ LV4 ring to RV coil/ring ◦ LV4 ring to Can
	descr.	DULVSA	(first) LV sensing amplitude [mV], mean value	scale	n.a.
	descr.	DULVPT01	(first) LV pacing threshold [V]	scale	n.a.
	descr.	DULVPTPW01	Pulse width for (first) LV pacing threshold measurements [ms]	scale	n.a.
	descr.	DULVPI01	(first) LV pacing impedance [Ω]	scale	n.a.

Lead measurements for the second vector are reported in chapter 9.2.3 Usage and settings of MultiPole pacing (MPP) .

Data file patient_ display_id_full	Notes	Variable name	Variable label	Variable level	Nominal values

8.2.5 Sensing and pacing assessment

CIP chapter 8.1.4.15 Lead measurements with Renamic programmer at implantation and each follow-up

The investigator is asked to assess the sensing and pacing performance at the end of each follow-up...

Lead Measurements / System performance RA

Data file PRVISIT & patient_ display_id_full	Notes	Variable name	Variable label	Variable level	Nominal values
lead_ measurement	descr.	DURASAAD	Adequate RA sensing	nominal	 Yes  No
	case listings for DURASAAD = No	DURASARE	Reason for inadequate RA sensing	nominal	 No intrinsic signal  Oversensing  Undersensing  Other
	descr.	DURAPCAD	Adequate RA pacing	nominal	 Yes  No
	case listings for DURAPCAD = No	DURAPCRE	Reason for inadequate RA pacing	nominal	 No overpacing possible  Exit block: no capture at maximum output  Other

Data file PRVISIT & patient_ display_id_full	Notes	Variable name	Variable label	Variable level	Nominal values
lead_ measurement	case listings for DURASARE =Other	CORASAOT	Specification of other reason for inadequate RA sensing	text	n.a.
	case listings for DURAPCRE=Other	CORAPCOT	Specification of other exit block for inadequate RA pacing	text	n.a.

Lead Measurements / System performance RV

Data file PRVISIT & patient_ display_id_full	Notes	Variable name	Variable label	Variable level	Nominal values
lead_ measurement	descr.	DURVSAAD	Adequate RV sensing	nominal	 Yes  No
	descr.	DURASARE	Reason for inadequate RV sensing	nominal	 No intrinsic signals  Oversensing  Undersensing  Other
	descr.	DURAPCAD	Adequate RV pacing	nominal	 Yes  No
	descr.	DURVPCRE	Reason for inadequate RV pacing	nominal	 No overpacing possible  Exit block: no capture at maximum output  Other

Data file PRVISIT & patient_ display_id_full	Notes	Variable name	Variable label	Variable level	Nominal values
lead_ measurement	case listings for DURVSARE=Other	CORVSAOT	Specification of other reason for inadequate RV sensing	text	n.a.
	case listings for DURVPCRE=Other	CORVPCOT	Specification of other exit block for inadequate RV pacing	text	n.a.

Lead Measurements / System performance LV

Data file PRVISIT & patient_ display_id_full	Notes	Variable name	Variable label	Variable level	Nominal values
lead_ measurement	descr.	DULVSAAD	Adequate LV sensing	nominal	 Yes  No
	descr.	DULVSARE	Reason for inadequate LV sensing	nominal	 No intrinsic signal  Oversensing  Undersensing  Other
	descr.	DULVPCAD	Adequate LV pacing	nominal	 Yes  No
	descr.	DULVPCRE	Reason for inadequate LV pacing	nominal	 No overpacing possible  Exit block: no capture at maximum output  Other

Data file PRVISIT & patient_ display_id_full	Notes	Variable name	Variable label	Variable level	Nominal values
lead_ measurement	case listings for DULVSARE=Other	COLVSAOT	Specification of other reason for inadequate LV sensing	text	n.a.
	case listings for DULVPCRE=Other	COLVPCOT	Specification of other exit block for inadequate LV pacing	text	n.a.

8.2.6 Arrhythmias and their treatment by the ICD/CRT-D system

CIP chapter 8.1.4.16 Tachyarrhythmia episodes

During the course of the study the following tachyarrhythmia episodes have to be recorded, analyzed and evaluated on the tachyarrhythmia episode form:

- All episodes detected in the VT-1, VT-2 or VF-zone
- All episodes with attempted and/or delivered therapies (ATP and/or shock)
- The first new and last two AF and/or SVT episodes between two follow-ups.

The appropriateness of the episode detection and the success of the delivered ATPs and/or shocks to terminate the episode will be evaluated...

Detection zone and assessment

Data file CEEPNUM	Notes	Variable name	Variable label	Variable level	Nominal values
tachy- arrhythmia_ episode	no report	CEEPNUM	Episode number	nominal	...  nsVT/nsT  ATR  SVT  VT1 / VT2  VF
	5 x7 table CEEPLOC x CEEPAS_corr_SAR	CEEPLOC	Detection zone	nominal	 AF  Atrial flutter  Sinus tachycardia  Other SVT  Non-sustained VT / VF  Sustained VT / VF  Oversensing / Other
	No report	CEEPAS	Episode assessment	nominal	 AF  Atrial flutter  Sinus tachycardia  Other SVT  Non-sustained VT / VF  Sustained VT / VF  Oversensing / Other
tachy- arrhythmia_ episode_SAR	5 x7 table CEEPLOC x CEEPAS_corr_SAR ³¹	CEEPAS_corr_SAR ³¹	Episode assessment - corrected	nominal	 AF  Atrial flutter  Sinus tachycardia  Other SVT  Non-sustained VT / VF  Sustained VT / VF  Oversensing / Other

Therapy in VF zone

Data file CEEPNUM	Notes	Variable name	Variable label	Variable level	Nominal values
tachy- arrhythmia_ episode	No report	DX1THAT01	First therapy delivered	nominal	 ATP one-shot  Shock  No therapy (shock charging aborted)
		DXATPOSA01	ATP one-shot successfully terminated the episode	nominal	 Yes  No
		DXSHKTOT01	Number of shocks delivered in VF zone	ordinal	n.a.
		DXSHKAS01	Shock(s) successfully terminated the episode in VF zone	nominal	 Yes  No
		CEEPOUT01	Episode outcome in VF zone	nominal	 Spontaneously self-terminated  Successful external defibrillation  Patient death  Other
		COEPOUT01	Specification episode outcome in VF zone	text	n.a.

Therapy in VT zone

Data file CEEPNUM	Notes	Variable name	Variable label	Variable level	Nominal values
tachy- arrhythmia_ episode	No report	DX1THAT02	First therapy delivered in VT zone	nominal	 ATP  Shock  No therapy (shock charging aborted)
		DXATPTOT02	Number of ATP attempts in VT zone	nominal	 n.a.
		DXATPRES02	ATP results in VT zone	nominal	 Episode terminated by ATP  Shock(s) delivered after ATP failure  No shock delivered after ATP failure
		DXSHKTOT02	Number of shocks delivered in VT zone	ordinal	n.a.
		DXSHKAS02	Shock(s) successfully terminated the episode in VT zone	nominal	 Yes  No
		CEEPOUT02	Episode outcome in VT zone	nominal	 Spontaneously self-terminated  Successful external defibrillation  Patient death  Other
		COEPOUT02	Specification episode outcome in VT zone	text	n.a.

Appropriateness of episode detection per episode

Appropriateness of episode detection will be evaluated with respect to the consequences the detection has on the delivery of an ICD therapy.

- Detection zones that (may) result in delivery of a therapy (depending on the programming): VT1/VT2 or VF
- Detection zone that will never result in the delivery of a therapy: nsVT/nsT, ATR, or SVT
- Rhythm (episode assessment) that requires a therapy: sustained VT/VF and non-sustained VT/VF (with successful therapy; see below)
- Rhythm (episode assessment) that does not require a therapy: The remaining options for episode assessment and non-sustained VT/VF (without successful therapy, see below)

[figure not shown]

	Rhythm that requires a therapy	Rhythm that does not require a therapy
Detection zone that (may) result in delivery of a therapy (depending on the programming)	Appropriate detection of ventricular arrhythmia (true positive)	Inappropriate detection (non-ventricular arrhythmia falsely detected; false positive)
Detection zone that will never result in the delivery of a therapy	Inappropriate detection (ventricular arrhythmia not detected; false negative)	Appropriate detection (non-ventricular arrhythmia correctly detected; true negative)

Data file patient_ display_id_full	Notes	Variable name	Variable label	Variable level	Nominal values
tachy- arrhythmia_ episode_SAR	descriptive; case listings for all fn and fp episodes	tp_episode_detection_SAR ³³	Appropriate detection of ventricular arrhythmia (true positive)	nominal	 1  0
		fn_episode_detection_SAR ³⁴	Inappropriate detection (ventricular arrhythmia not detected; false negative)	nominal	 1  0
		tn_episode_detection_SAR ³⁵	Appropriate detection (non-ventricular arrhythmia correctly detected; true negative)	nominal	 1  0
		fp_episode_detection_SAR ³⁶	Inappropriate detection (non-ventricular arrhythmia falsely detected; false positive)	nominal	 1  0

The episode detection is evaluated by the following values:

- Sensitivity = sum tp / (sum tp + sum fn)
- Specificity = sum tn / (sum tn + sum fp)
- PPV = sum tp / (sum tp + sum fp)
- NPV = sum tn / (sum tn + sum fn)

Appropriateness of episode detection per patient

Data file patient_ display_id_full	Notes	Variable name	Variable label	Variable level	Nominal values
data_SAR	descri ptive	any_tachy_detection_SAR ³⁷	Any tachy-arrhythmia episode with non-missing information about the detection zone	nominal	 Yes  No
		any_tachy_detection_VTVF_SAR ³⁸	Any tachy-arrhythmia episode with detection in the VT1/VT2 or VF zone	nominal	 Yes  No
		only_tachy_app_detection_SAR ³⁹	All tachy-arrhythmia episodes with appropriate detection (all true positive or true negative)	nominal	 Yes  No
		any_tachy_inapp_detection_SAR ⁴⁰	Any tachy-arrhythmia episode with inappropriate detection (any false positive or false negative)	nominal	 Yes  No

ATP efficacy per tp episode

Only applicable for true positive tachy-arrhythmia episodes⁴¹ as defined before.

Data file patient_ display_id_full	Notes	Variable name	Variable label	Variable level	Nominal values
tachy- arrhythmia_ episode_SAR	descri ptive	tpVF_ATP_SAR ⁴²	True positive episode in VF zone with ATP-one-shot therapy	nominal	 1  0
		tpVF_ATP_success_SAR ⁴³	True positive episode in VF zone with successful ATP-one-shot therapy	nominal	 1  0

Data file patient_ display_id_full	Notes	Variable name	Variable label	Variable level	Nominal values
tachy- arrhythmia_ episode_SAR	descri ptive	tpVT_ATP_SAR ⁴⁴	True positive episode in VT1/VT2 zone with at least one ATP therapy	nominal	 1  0
		tpVT_ATP_success_SAR ⁴⁵	True positive VT1/VT2 episode with successful ATP therapy	nominal	 1  0
		n_ATP_tpVT_SAR ⁴⁶	Number of ATP-attempts per true positive VT1/VT2 episode	Metric reported as nominal	 1  2 ...

The ATP efficacy is evaluated by the following values:

- ATP VF efficacy rate = sum{VFtp_ATP_success_SAR}/ sum{VFtp_ATP_SAR}
- ATP VT efficacy rate = sum{VTtp_ATP_success_SAR}/ sum{VTtp_ATP_SAR}

ATP efficacy per patient (for tp episodes)

Only applicable patients with any true positive tachy-arrhythmia episodes⁴⁷ as defined before.

Data file patient_ display_id_full	Notes	Variable name	Variable label	Variable level	Nominal values
data_SAR	descriptive	any_tpVF_ATP_SAR ⁴⁸	Any true positive VF episode with ATP one-shot therapy	nominal	 Yes  No
		only_tpVF_noATP_SAR ⁴⁹	All true positive VF episodes without ATP one-shot therapy	nominal	 Yes  No
		only_tpVF_ATP_success_SAR ⁵⁰	All true positive VF episodes with ATP one-shot therapy were successful	nominal	 Yes  No
		any_tpVF_ATP_nosuccess_SAR ⁵¹	Any true positive VF episode with delivered but not successful ATP one-shot therapy	nominal	 Yes  No
		any_tpVT_ATP_SAR ⁵²	Any true positive VT episode with ATP therapy	nominal	 Yes  No
		only_tpVT_noATP_SAR ⁵³	All true positive VT episodes without ATP therapy	nominal	 Yes  No
		only_tpVT_ATP_success_SAR ⁵⁴	All true positive VT episodes with ATP therapy were successful	nominal	 Yes  No
		any_tpVT_ATP_nosuccess_SAR ⁵⁵	Any true positive VT episode with delivered but not successful ATP therapy	nominal	 Yes  No

Shock efficacy per tp episode

Only applicable for true positive tachy-arrhythmia episodes⁵⁶ as defined before.

Data file patient_ display_id_full	Notes	Variable name	Variable label	Variable level	Nominal values
tachy- arrhythmia_ episode_SAR	descri ptive	tpVF_shock_SAR ⁵⁷	True positive episode in VF zone with at least one shock therapy	nominal	 1  0
		tpVF_shock_success_SAR ⁵⁸	True positive episode in VF zone with successful shock therapy	nominal	 1  0
		n_shock_tpVF_SAR ⁵⁹	Number of shocks per true positive episode in VF zone	Metric reported as nominal	 1  2 ...
		tpVT_shock_SAR ⁶⁰	True positive episode in VT zone with at least one shock therapy	nominal	 1  0
		tpVT_shock_success_SAR ⁶¹	True positive episode in VT zone with successful shock therapy	nominal	 1  0
		n_shock_tpVT_SAR ⁶²	Number of shocks per true positive episode in VT zone	Metric reported as nominal	 1  2 ...

The shock efficacy is evaluated by the following values:

- Shock VF efficacy rate = $\text{sum}\{\text{tpVF_shock_success_SAR}\} / \text{sum}\{\text{tpVF_shock_SAR}\}$
- Shock VT efficacy rate = $\text{sum}\{\text{tpVT_shock_success_SAR}\} / \text{sum}\{\text{tpVT_shock_SAR}\}$

Shock efficacy per patient (for tp episodes)

Only applicable for patients with any true positive tachy-arrhythmia episodes⁶³ as defined before.

Data file patient_ display_id_full	Notes	Variable name	Variable label	Variable level	Nominal values
data_SAR	descri ptive	any_tpVF_shock_SAR ⁶⁴	Any true positive VF episode with shock therapy	nominal	 Yes  No
		only_tpVF_noshock_SAR ⁶⁵	All true positive VF episodes without shock therapy	nominal	 Yes  No
		only_tpVF_shock_success_SAR ⁶⁶	All true positives VF episodes with shock therapy were successful	nominal	 Yes  No
		any_tpVF_shock_nosuccess_SAR ⁶⁷	Any true positive VF episode with not successful shock therapy	nominal	 Yes  No
		any_tpVF_shock_SAR ⁶⁸	Any true positive VT episode with shock therapy	nominal	 Yes  No
		only_tpVF_noshock_SAR ⁶⁹	All true positive VT episodes without shock therapy	nominal	 Yes  No
		only_tpVF_shock_success_SAR ⁷⁰	All true positive VT episodes with shock therapy were successful	nominal	 Yes  No
		any_tpVF_shock_nosuccess_SAR ⁷¹	Any true positive VT episode with not successful shock therapy	nominal	 Yes  No

Therapy efficacy per patient (for tp episodes)Only applicable for patients with any true positive tachy-arrhythmia episodes⁷² as defined before.

Data file patient_ display_id_full	Notes	Variable name	Variable label	Variable level	Nominal values
data_SAR	descri ptive	any_tpVF_therapy_SAR ⁷³	Any true positive VF episode with ATP or shock therapy	nominal	 Yes  No
		only_tpVF_therapy_success_SAR ⁷⁴	All true positive VF episodes with ATP or shock therapy were successful	nominal	 Yes  No
		any_tpVF_therapy_nosuccess_SAR ⁷⁵	Any true positive VF episode with not successful shock or ATP therapy	nominal	 Yes  No
data_SAR	descri ptive	any_tpVT_therapy_SAR ⁷⁶	Any true positive VT episode with ATP or shock therapy	nominal	 Yes  No
		only_tpVT_therapy_success_SAR ⁷⁷	All true positive VT episodes with ATP and shock therapy were successful	nominal	 Yes  No
		any_tpVT_therapy_nosuccess_SAR ⁷⁸	Any true positive VT episode with not successful ATP or shock therapy	nominal	 Yes  No

Inappropriate therapies per fp episode

Only applicable for false positive tachy-arrhythmia episodes⁷⁹ as defined before.

Data file patient_display_id_full	Notes	Variable name	Variable label	Variable level	Nominal values
tachy- arrhythmia_ episode_SAR	descri ptive	fp_episode_ATP_SAR ⁸⁰	False positive episode with inappropriate ATP or ATP one-shot therapy	nominal	 1  0
		fp_episode_shock_SAR ⁸¹	False positive episode with inappropriate shock therapy	nominal	 1  0
		fp_episode_ATP_shock_SAR ⁸²	False positive episode with inappropriate ATP, ATP-one-shot, or shock therapy	nominal	 1  0

Data file patient_display_id_full	Notes	Variable name	Variable label	Variable level	Nominal values
tachy- arrhythmia_ episode_SAR	descri ptive or case listing	n_ATP_fp_episode_SAR ⁸³	Number of inappropriate ATPs (ATP one-shot counts as 1) per false positive episode	Metric reported as nominal	 1  2  ...
		n_shock_fp_episode_SAR ⁸⁴	Number of inappropriate shocks per false positive episode	Metric reported as nominal	 1  2  ...
		n_ATP_shock_fp_episode_SAR ⁸⁵	Number of inappropriate ATPs (ATP one-shot counts as 1) or shocks per false positive episode	Metric reported as nominal	 1  2 ...

Inappropriate therapies per patient (for fp episodes)

Only applicable for patients with any false positive tachy-arrhythmia episodes⁸⁶ as defined before.

Data file patient_ display_id_full	Notes	Variable name	Variable label	Variable level	Nominal values
data_SAR	descri ptive	any_fp_ATP_therapy_SAR ⁸⁷	Any false positive episode with inappropriate ATP therapy	nominal	 Yes  No
		any_fp_shock_therapy_SAR ⁸⁸	Any false positive episode with inappropriate ATP or shock therapy	nominal	 Yes  No
		any_fp_ATP_shock_therapy_SAR ⁸⁹	Any false positive VF episode with inappropriate ATP or shock therapy	nominal	 Yes  No

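### As visibly worded, SAP 8.2.6 drops non-sustained VT/VF treated without success from the therapy-efficacy denominators and labels it non-ventricular (minor; descriptive data only)

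*SAP*

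**What the plan says.** SAP 8.2.6 gives the purpose of the classification: "Appropriateness of episode detection will be evaluated with respect to the consequences the detection has on the delivery of an ICD therapy". It then splits rhythms in two.

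- Needing therapy: "Rhythm (episode assessment) that requires a therapy: sustained VT/VF and non-sustained VT/VF (with successful therapy; see below".
- Not needing therapy: "The remaining options for episode assessment and non-sustained VT/VF (without successful therapy, see below".

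Zones are split as well. VT1/VT2 and VF may lead to therapy. The rest are covered by "Detection zone that will never result in the delivery of a therapy: nsVT/nsT, ATR, or SVT".

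Crossing the two splits gives four cells. The false-positive cell reads "Inappropriate detection (non-ventricular arrhythmia falsely detected; false positive" and the true-negative cell reads "Appropriate detection (non-ventricular arrhythmia correctly detected; true negative".

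Later tables of the same section restrict ATP, shock and overall therapy efficacy to true-positive episodes, or to patients who have them. ATP or shock in a false-positive episode is tabulated as inappropriate therapy.

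The section also plans a 5x7 table of detection zone by corrected episode assessment, and case listings of all false-negative and false-positive episodes. SAP 8.6 states that there are no hypotheses for these data. Protocol 8.1.4.16 requires every treated episode to be recorded and promises an evaluation of whether the delivered ATPs and shocks ended the episode.

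**The concern.** For sustained VT/VF, therapy outcome plays no part in the classification. For non-sustained VT/VF it decides the cell. A success enters the efficacy numerator and denominator, while a failure enters neither and reappears as inappropriate therapy. A success rate whose denominator depends on success does not measure how well the therapy works.

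The labels add a second fault. A rhythm that the investigator assessed as VT/VF would be reported as a non-ventricular arrhythmia. That would mix it with therapy for AF, SVT or oversensing, where inappropriate therapy has its usual meaning.

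**Working it through.** The plan states no figure for this analysis, so there is nothing to reproduce. The check applies the visible rule to every case and then puts assumed counts into the SAP's own ratios.

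**1. Where each episode falls**

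| Zone | Assessed rhythm | Therapy | Cell |
|---|---|---|---|
| VT1/VT2 or VF | Sustained VT/VF | any or none | TP |
| VT1/VT2 or VF | Non-sustained VT/VF | successful | TP |
| VT1/VT2 or VF | Non-sustained VT/VF | given, no success | FP |
| VT1/VT2 or VF | Non-sustained VT/VF | none | FP |
| VT1/VT2 or VF | AF, SVT, other | any or none | FP |
| nsVT/nsT, ATR, SVT | Sustained VT/VF | none | FN |
| nsVT/nsT, ATR, SVT | Non-sustained VT/VF | none | TN |

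Rows 3 and 4 carry the non-ventricular label of the FP cell, and row 7 that of the TN cell. Row 3 is the one that leaves the efficacy denominator.

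**2. Can row 3 occur?** The episode form allows it. The VT-zone items include "No shock delivered after ATP failure", and the outcome items for both zones include "Spontaneously self-terminated".

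**3. Effect on counts (all counts assumed).** Take 20 sustained VT/VF treated with ATP, of which 14 succeed, plus 10 non-sustained VT/VF treated with ATP, and no rescue by shock.

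- With 5 of the 10 successful, the SAP rule gives (14+5)/(20+5) = 19/25 = 76.0%. All treated VT/VF gives 19/30 = 63.3%, and sustained only gives 14/20 = 70.0%. Five episodes become inappropriate therapy.
- With 8 of the 10 successful, the SAP rule gives 22/28 = 78.6%, against 22/30 = 73.3%. Two episodes become inappropriate therapy.
- With no non-sustained failure, the two rates agree.

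**4. General form for ATP.** Let p be ATP success (taken as equal in sustained and non-sustained episodes), s the non-sustained share of ATP-treated VT/VF, and r the share of failed ATPs later ended by shock. Successful therapy is read as any therapy, so a rescued episode stays a true positive and counts as an ATP failure. Efficacy among all treated is p. The SAP rule gives

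p / (1 − s(1−p)(1−r)).

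The documents give no values for s, p or r. Over an assumed s of 0.05 to 0.33 and p of 0.60 to 0.90, the extremes are:

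| r | s=0.05, p=0.90 | s=0.33, p=0.60 |
|---|---|---|
| 0 | 0.900/0.995 = 0.9045 (+0.5 points) | 0.600/0.868 = 0.6912 (+9.1) |
| 0.5 | 0.900/0.9975 = 0.9023 (+0.2) | 0.600/0.934 = 0.6424 (+4.2) |
| 0.9 | 0.900/0.9995 = 0.9005 (under 0.1) | 0.600/0.9868 = 0.6080 (+0.8) |
| 1 | 0 | 0 |

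The sign is fixed: the denominator factor cannot exceed 1, so the SAP rate is never below p. The size depends entirely on the inputs.

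**The case against.** The strongest reply is that the operative rule may not be fully in view. Both clauses point to text below them, a figure follows that is not shown, and the footnotes that code the corrected assessment and the four cells cannot be read. That stands as a limit: this point concerns the visible wording only.

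Second, the rule has a rationale. An episode that stopped by itself after failed therapy arguably did not need therapy, whereas one ended by therapy cannot be shown to have been self-limiting. This can defend crediting successes when detection is judged. It does not defend a success rate that keeps non-sustained successes and drops non-sustained failures, nor does it make an assessed VT/VF non-ventricular.

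Third, the rule does not simply favour the device, since each dropped failure becomes a false positive and lowers PPV and specificity. That is correct, but an error in one summary does not repair another.

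Fourth, the planned safeguards are real. The 5x7 table separates non-sustained VT/VF from AF, flutter, sinus tachycardia, other SVT and oversensing within each zone, and every false positive is listed. A reader can therefore rebuild the non-sustained part of the false-positive cell. The summary rates and labels would still stand uncorrected.

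Finally, few episodes may be affected. In the predecessor study (protocol 5.2.2), 5 patients of a 111-patient group had a protocol-specified one-shot ATP attempt.

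**Conclusion.** The point holds for the visible wording and is minor. Relative to all treated VT/VF, efficacy is overstated or unchanged. The size is unknown, and it is zero for ATP if every failed ATP is followed by a successful shock. The figures in the working are illustrations on assumed inputs.

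A reader might infer more, and the documents do not support it:

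- *That reported efficacy will be inflated by a known amount.* No episode counts are given. The predecessor results cannot supply them: the one-shot result (1 of 5) and the conversion result with lower limit 0.977 (protocol 5.2.1) are per patient, while these ratios are per episode.
- *That failures are concealed or a safety conclusion is at risk.* The zone-by-assessment table and the listings expose the cases. The data are descriptive, and no primary or secondary endpoint uses them.
- *That sensitivity and specificity are biased by the recording rule.* Only the first new and last two AF and/or SVT episodes per interval are required, and untreated nsVT/nsT-zone episodes are not listed. Bias arises only if sites record no more than this and further episodes occurred. The rule is printed at the head of the same SAP section, so this calls for a reporting note at most.

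**What to change.** In SAP 8.2.6:

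1. Define the ATP, shock and overall efficacy denominators by episode assessment, not by therapy outcome. Report each on (a) all treated episodes assessed as VT/VF and (b) sustained VT/VF only.
2. Relabel the false-positive and true-negative cells as rhythm not requiring therapy, so that no assessed VT/VF is called non-ventricular.
3. Show treated non-sustained VT/VF on its own line, apart from inappropriate therapy for non-ventricular rhythms.

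Optionally, note that sensitivity, specificity and NPV are among recorded episodes. If the unseen figure or footnotes already do any of this, bring the visible text into line with them.

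The cost is SAP wording and programming. No new data are needed, because all treated episodes must already be recorded. The downside is that efficacy figures may be slightly lower and the tables slightly longer.

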8.1.4.16 Tachyarrhythmia episodes

During the course of the study the following tachyarrhythmia episodes have to be recorded, analyzed and evaluated on the tachyarrhythmia episode form:

- All episodes detected in the VT-1, VT-2 or VF-zone
- All episodes with attempted and/or delivered therapies (ATP and/or shock)
- The first new and last two AF and/or SVT episodes between two follow-ups.

The appropriateness of the episode detection and the success of the delivered ATPs and/or shocks to terminate the episode will be evaluated. The corresponding IEGM should be stored by opening it manually and provided to the sponsor (see section 8.1.4.19). In case of new onset of AF, the investigator will be asked if the episode was detected by Home Monitoring prior to the follow-up.

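### Sensitivity, specificity and NPV for arrhythmia detection combine fully recorded positive episodes with partly recorded negative ones (SAP 8.2.6, Protocol 8.1.4.16)

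*SAP*

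**What the plan says.** Protocol 8.1.4.16, repeated in SAP 8.2.6, lists what goes on the tachyarrhythmia episode form:

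- "All episodes detected in the VT-1, VT-2 or VF-zone"
- "All episodes with attempted and/or delivered therapies (ATP and/or shock" (closing bracket not shown)
- "The first new and last two AF and/or SVT episodes between two follow-ups"

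SAP 8.2.6 then classes each recorded episode by detection zone and by assessed rhythm. VT1/VT2 and VF are the zones that can lead to therapy. The others form the negative side: "Detection zone that will never result in the delivery of a therapy: nsVT/nsT, ATR, or SVT". Crossing zone with rhythm gives true and false positives (tp, fp) and true and false negatives (tn, fn).

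From these the SAP computes "Sensitivity = sum tp / (sum tp + sum fn" and "Specificity = sum tn / (sum tn + sum fp" (closing brackets not shown), with PPV and NPV built in the same way. Therapy success is also a ratio of sums. For ATP the SAP writes "The ATP efficacy is evaluated by the following values" and lists, for example, "ATP VF efficacy rate = sum{VFtp_ATP_success_SAR}/ sum{VFtp_ATP_SAR" (closing brace not shown).

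Beside the episode-level rates, the SAP plans per-patient any/all tables for detection, ATP, shock and inappropriate therapy, and case listings of all fn and fp episodes. Intervals are specified only for the primary endpoint (SAP 5.2, 11.6) and the Kaplan-Meier endpoint (SAP 12.6).

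**The concern.** Sensitivity and specificity each need numerator and denominator to be drawn from the same pool of episodes. Here sensitivity sets a complete tp count against a partial fn count, and specificity sets a partial tn count against a complete fp count. The ratios therefore depend on the recording rule as well as on the device.

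For a defibrillator, the share of ventricular arrhythmias recognised is a figure that readers will take at face value. Protocol 7.1 says that performance is to be assessed and that results will update the clinical evaluation and supply authorities outside the CE region. A sensitivity raised by unrecorded misses would flatter the device, and a specificity lowered by unrecorded true negatives would do it an injustice.

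**Working it through.** The plan gives no episode count, precision target or sample size for this section, so there is no planned figure to reproduce. The only sample size, 114 evaluable and 127 enrolled (Protocol 11.2), belongs to the primary endpoint and does not depend on this point.

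**Step 1: which rule feeds which cell.**

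- tp and fp come from VT1/VT2/VF-zone detections. The first recording rule covers all of them.
- tn and fn come from nsVT/nsT, ATR and SVT detections. The SAP says these zones never lead to therapy, so the treated-episode rule adds nothing. What remains is the AF/SVT rule, which is capped at about three episodes per interval. No rule is stated for untreated nsVT/nsT.

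**Step 2: direction.** Let a be the recorded share of fn and b the recorded share of tn.

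- Sensitivity = tp/(tp + a·fn). It rises as a falls and does not depend on b.
- Specificity = b·tn/(b·tn + fp). It falls as b falls.
- NPV = b·tn/(b·tn + a·fn). It is unchanged only if a = b. A first-and-last selection is not random, so a = b cannot be presumed.
- PPV = tp/(tp + fp). It contains neither a nor b.

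**Step 3: illustration.** Assumed counts, not from the documents: tp 40, fp 10, tn 300, fn 5.

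| a / b | Sensitivity | Specificity | NPV |
|---|---|---|---|
| 100% / 100% | 40/45 = 88.9% | 300/310 = 96.8% | 300/305 = 98.4% |
| 25% / 25% | 40/41.25 = 97.0% | 75/85 = 88.2% | 75/76.25 = 98.4% |
| 100% / 25% | 40/45 = 88.9% | 75/85 = 88.2% | 75/80 = 93.8% |
| 0% / 25% | 40/40 = 100% | 75/85 = 88.2% | 75/75 = 100% |

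PPV is 40/50 = 80% in every row. Row 3 shows that sensitivity does not move if every missed VT/VF is recorded.

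**Step 4: range.** A second assumed set (tp 90, fn 10, tn 900, fp 100; both rates truly 90%), with a = b:

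- at 0.5: 90/95 = 94.7% and 450/550 = 81.8%
- at 0.2: 90/92 = 97.8% and 180/280 = 64.3%
- at 0.1: 90/91 = 98.9% and 90/190 = 47.4%

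**Step 5: the secondary point, pooling.** Assume one patient with 30 successes in 30 episodes and ten patients each with 1 success in 2. The pooled rate is 40/50 = 80%. The mean of the per-patient proportions is (1 + 10 × 0.5)/11 = 54.5%. The planned table would show all episodes successful in 1 of 11 patients and at least one failure in 10 of 11.

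**The case against.** The strongest reply is that little is lost in practice. A patient with three or fewer AF/SVT episodes in an interval may lose nothing, sites may record more than the minimum, and nothing in the documents supports a 25% recording share. Every recorded fn and fp episode is listed individually, so a recorded miss cannot hide behind a ratio. These are further data of interest (Protocol 7.5.1) with no hypothesis (SAP 8.6), and SAP 5.3 treats everything outside the primary endpoint as exploratory. All of that stands, and it limits the weight of the point. It does not remove the mismatch: the listings cannot show an episode that was never recorded, and the formulas carry no caveat.

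A reader might go further and infer that the SAP makes no allowance for repeated episodes within a patient. It does make some: the any/all tables count each patient once and show how many patients had any treated episode. They are coarse, since 29 of 30 successes and 0 of 30 both score as not all successful, but they would expose the dominance in Step 5.

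A reader might also infer that clustering invalidates the planned precision, since five episodes per patient with an assumed within-patient correlation of 0.5 give a design effect of 1 + 4 × 0.5 = 3. No interval or test is planned for these rates, so none is miscalibrated. The patient-averaged rate is also a different quantity, not a corrected one.

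**Conclusion.** The point holds in limited form. Followed as written, SAP 8.2.6 yields a specificity that is too low whenever true negatives go unrecorded, a sensitivity that is too high whenever missed VT/VF is among the unrecorded episodes, and an NPV that can move either way. PPV and the ATP and shock efficacy rates are not affected by the recording rule.

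The size cannot be stated. The movements from 88.9% to 97.0% and from 96.8% to 88.2% rest on assumed counts and an assumed 25% recording share. For nsVT/nsT, partial recording is inferred from the absence of a rule. The footnoted derivations in SAP 8.2.6 could not be checked, and they may hold selection details.

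It would be wrong to read this as a threat to the trial's safety conclusion. That conclusion rests on adjudicated SADEs. The primary endpoint, the sample size and the pass/fail rule are unaffected. The missing intervals and the pooling are a secondary matter of presentation.

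**What to change.** In SAP 8.2.6, either drop sensitivity, specificity and NPV, or report them only as values among recorded episodes, with the recording rule of Protocol 8.1.4.16 stated beside them and no device-performance conclusion drawn. Keep PPV and the fn/fp case listings.

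Optional: beside each pooled ATP, shock and PPV rate, print the number of contributing patients and the mean of the per-patient proportions. Add a patient-level interval only where enough patients contribute. In the predecessor study (Protocol 5.2.2), ATP one-shot was attempted in 5 patients and succeeded in 1, for which the exact 95% interval is 0.5% to 71.6%. With so few patients GEE is unreliable, and at 100% success a cluster bootstrap has zero width.

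Protocol 11.8 allows the SAP to be updated before database freeze or closure, and no new data are needed. The cost is slightly more programming and a sensitivity figure that is omitted or looks less favourable.
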